19. **Avelumab Administration:** Treatment will be administered every 2 weeks in 4-week cycles (ie, 28-day cycles). Avelumab will be administered as a 1-hour intravenous infusion every 2 weeks (eg, on Days 1, 15 of a cycle). For all cohorts except Cohort A9, avelumab administration will start on Cycle 1 Day 1. For patients randomized to Cohort A9, avelumab administration will begin on Cycle 2 Day 1. Avelumab infusion will start at least 30 minutes (+20 minute time window, if needed) after completion of utomilumab infusion. On days when PK samples are taken, avelumab infusion will start after the post- utomilumab and pre-avelumab pharmacokinetic blood samples are drawn. Treatment will continue until disease progression is confirmed by the investigator, patient refusal, unacceptable toxicity, or until the study is terminated by the Sponsor, whichever occurs first. See [Section 5.3.5.3](#) for details of treatment after initial determination of radiological disease progression.
20. **Utomilumab Administration:** Treatment will be administered in a 4-week cycle (ie, 28-day cycle). Utomilumab will be administered as a 1-hour intravenous infusion on Day 1 of a cycle. For all cohorts except Cohort A10, utomilumab administration will start on Cycle 1 Day 1. For patients randomized to Cohort A10, utomilumab administration will begin on Cycle 2 Day 1. When both utomilumab-and avelumab are administered, utomilumab will be administered first, followed by the avelumab infusion at least 30 minutes (+20 minute time window, if needed) after the end of the utomilumab infusion. Treatment will continue until disease progression is confirmed by the investigator, patient refusal, unacceptable toxicity, or until the study is terminated by the Sponsor, whichever occurs first. See [Section 5.3.5.3](#) for details of treatment after initial determination of radiological disease progression.

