25. **Survival:** Patients will be followed for survival, independently of time of disease progression or initiation of subsequent anticancer therapy, for at least 2 years after randomization of the last patient in the randomized cohorts and for at least 2 years after first dose of the last patient for the non-randomized cohorts unless lost to follow-up, consent withdrawal, or study discontinued by the Sponsor. Patients will be contacted every 3 months for survival status and subsequent anti-cancer treatment.
26. **Blood for Utomilumab Pharmacokinetics:** Blood samples (3.5 mL whole blood at each time point) will be collected from all patients in the study at pre dose and 1 hour (ie, at the end of infusion) on Day 1 of Cycles 1, 3, 5, 8, and Cycle 12. A sample will also be collected on Days 8 and 15 of Cycle 1 (non-dosing visit). For patients randomized to Cohort A9, PK samples will begin on Cycle 1 Day 1. For patients randomized to Cohort A10, PK samples will begin on Cycle 3 Day 1.
27. **Blood for Avelumab Pharmacokinetics:** Blood samples (3.5 mL whole blood at each time point) will be collected from all patients in the study at pre dose and 1 hour post-infusion (ie, at the end of infusion) on Days 1 and 15 of Cycle 1, and then on Day 1 of Cycles 2, 4, 6, and Cycle 10. A sample will also be collected on Day 8 of Cycle 1 (non-dosing visit). For patients randomized to Cohort A9, PK samples will begin on Cycle 2 Day 1. For patients randomized to Cohort A10, PK samples will begin on Cycle 1 Day 1.
28. **Archival FFPE Tumor Tissue Block:** Patients in Phase 1b should provide archival FFPE tumor tissue if available. Patients in Phase 2 must provide FFPE tissue from the most recent primary or metastatic tumor biopsy or resection prior to study entry, taken within one year of start of study treatment, with no intervening systemic anti-cancer therapy; if such tissue is not available then a de novo biopsy prior to study entry is required. The requirement for archival tissue may be waived if a de novo biopsy will be collected. See [Section 6.1.1](#) and Laboratory Manual for additional details on the selection of lesions and preparation of tissue samples.

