35. **Banked Biospecimens:** A 4 mL blood biospecimen Prep D1 (K₂ ethylenediaminetetraacetic acid [EDTA] whole blood collection optimized for DNA analysis) will be collected on Day 1 of Cycle 1 prior to dosing and retained in a biobank for possible pharmacogenomic assessments, unless prohibited by local regulations or by decision of the IRB or EC (see also [Section 7.5](#) of the protocol).
36. **Blood for Utomilumab Immunogenicity (ADA) Testing:** Blood samples (3.5 mL whole blood at each time point) for utomilumab immunogenicity testing will be collected on Cycles 1, 3, 5, 8, and 12 on Day 1 at pre-dose. For patients randomized to Cohort A9, ADA samples will begin on Cycle 1 Day 1. For patients randomized to Cohort A10, ADA samples will begin on Cycle 3 Day 1.
37. **Blood for Avelumab Immunogenicity (ADA) Testing:** Blood samples (3.5 mL whole blood at each time point) for avelumab immunogenicity testing will be collected on Cycles 1, 2, 4, 6, and 10 on Day 1 at pre-dose. For patients randomized to Cohort A9, ADA samples will begin on Cycle 2 Day 1. For patients randomized to Cohort A10, ADA samples will begin on Cycle 1 Day 1.
38. **End of Treatment:** Obtain these assessments if not completed during the previous week on study, except for tumor assessments, which need not be repeated if performed within the prior 4 weeks. The EOT visit should occur within 7 days after discontinuation criteria are met.
39. **Follow-Up:** Patients should be evaluated for safety up to 90 days (30 days, 60 days, and 90 days) after last dose of investigational products. See [Section 6.3](#). Patients continuing to experience toxicity following discontinuation of investigational products will continue to be followed at least every 4 weeks regardless of initiation of new anticancer treatment until resolution or determination, in the clinical judgment of the Investigator, that no further improvement is expected. Patients whose disease has not progressed at the time of study treatment discontinuation will enter into disease follow-up. (For tumor assessment). Physical examination, ECOG status, vital signs, and safety laboratory measurements are not required for patients who initiate new anticancer treatment, unless the patient continues to experience toxicity following discontinuation of the investigational products. Contraception check and serum/urine pregnancy tests are required for all patients who enter Follow-up regardless of initiation of subsequent anticancer therapy.

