1.2.2.6. Immunogenicity of Utomilumab in Humans

Study B1641001

Based on preliminary data from Study B1641001, 9 of 61 (14.8%) patients in Portion A exhibited positive ADAs prior to treatment with utomilumab. Thirty-five out of 61 patients (57.4%) were positive for ADA for at least one time point regardless of baseline ADA status. Among 35 ADA-positive patients, 7 (20%) exhibited positive neutralizing antibody (Nab) against PF- 05082566 In Portion B, 2 out of 41 (4.9%) patients exhibited positive ADA against utomilumab prior to treatment with utomilumab plus rituximab. Three of 41 patients (7.3%) were positive for ADA for at least one time point regardless of baseline ADA status when administered in combination with rituximab. Among 3 ADA-positive patients, 1 (33.3%) exhibited positive Nab against utomilumab.

The impact of ADA on PK of utomilumab was also characterized. The utomilumab CL was similar in ADA negative and ADA positive patients suggesting that ADA status has minimal impact on the PK of utomilumab.

Study B1641003

Preliminary ADA data show 2 of 23 (8.7%) patients exhibited positive ADA against utomilumab prior to treatment with utomilumab plus pembrolizumab. Seventeen of 23 patients (73.9%) were positive for ADA for at least one time point regardless of baseline ADA status when administered in combination with pembrolizumab. Among 14 ADA positive patients who were tested for Nab analysis, 5 (35.7%) patients had a positive Nab against utomilumab. Complete pre-clinical and clinical information for utomilumab, including PK data in patients, may be found in the SRSD, which for this study is the utomilumab IB.²⁰

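### Cohort A10 starts utomilumab on Cycle 2 Day 1, but its utomilumab PK and ADA sampling starts on Cycle 3 Day 1, so the footnotes leave no pre-dose ADA sample and no first-dose Cmax (secondary endpoints, one closed cohort)

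*Protocol*

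**What the plan says.** Footnote 20 to the Combination A Schedule of Activities, repeated in Section 5.3.5.1, fixes the first dose: "For patients randomized to Cohort A10, utomilumab administration will begin on Cycle 2 Day 1".

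Utomilumab sampling follows a general grid. Footnote 36 sets the ADA days: "utomilumab immunogenicity testing will be collected on Cycles 1, 3, 5, 8, and 12 on Day 1 at pre-dose". Footnote 26 sets the PK days: "at pre dose and 1 hour (ie, at the end of infusion) on Day 1 of Cycles 1, 3, 5, 8, and Cycle 12", with extra PK samples on Days 8 and 15 of Cycle 1. Neither list contains Cycle 2.

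Both footnotes then add a rule for A10. Footnote 36 says "For patients randomized to Cohort A10, ADA samples will begin on Cycle 3 Day 1" and footnote 26 says "For patients randomized to Cohort A10, PK samples will begin on Cycle 3 Day 1".

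The mirror case is Cohort A9, which receives utomilumab alone in Cycle 1. Footnote 19 says "For patients randomized to Cohort A9, avelumab administration will begin on Cycle 2 Day 1", and footnotes 27 and 37 start A9's avelumab PK and ADA sampling on that same day.

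Table 4 marks Cycle 1 Day 1 for utomilumab PK and ADA with no exception for A10, whereas Table 3 does print cohort exceptions in its dosing rows.

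Section 2.2 makes Cmax, Ctrough and ADA levels secondary endpoints. Section 9.5.1 summarises Cmax and Ctrough by dose, cycle and day and plans an accumulation ratio. Section 9.5.4 plans the percentage of ADA-positive patients by dose and, data permitting, titer, onset and duration.

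**The concern.** The utomilumab grid was written for cohorts that start utomilumab in Cycle 1. Moving A10's first dose to Cycle 2 without adding a Cycle 2 sample leaves its first exposure unsampled. Three things follow.

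- **ADA.** A positive result on Cycle 3 Day 1 cannot be separated into antibody present before utomilumab and antibody induced by it, and onset has no starting point. Pre-existing antibody is not hypothetical: Section 1.2.2.6 reports "9 of 61 (14.8%) patients in Portion A exhibited positive ADAs prior to treatment with utomilumab".
- **Cmax.** No utomilumab end-of-infusion sample is scheduled at A10's first dose, so an accumulation ratio based on Cmax lacks its denominator.
- **Labelling.** Under a summary by dose, cycle and day, A10's Cycle 3 Day 1 values share a row with those of any cohort on the same utomilumab dose that is one administration further on.

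**Working it through.** The plan gives no figure to reproduce here; the check is one of dates, followed by a simple expected count.

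**Dates.** Cycles last 28 days (Section 3.2), so nominal study day = (cycle − 1) × 28 + day. Cycle 2 Day 1 is day 29 and Cycle 3 Day 1 is day 57.

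| Cohort | Drug | First dose | First sample per footnotes | Gap |
|---|---|---|---|---|
| A9 | utomilumab | day 1 | day 1 | 0 days |
| A9 | avelumab | day 29 | day 29 | 0 days |
| A10 | avelumab | day 1 | day 1 | 0 days |
| A10 | utomilumab | day 29 | day 57 | 28 days |

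Three of the four pairs have no gap. The protocol gives no reason for the fourth.

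**Does any scheduled utomilumab sample cover day 29?** The Day 1 grid for Cycles 1, 3, 5, 8 and 12 falls on days 1, 57, 113, 197 and 309. Day 29 is absent. The extra PK samples on days 8 and 15 precede A10's first utomilumab dose.

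**What Cycle 3 Day 1 measures.**

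| Sample on Cycle 3 Day 1 | Cohort A10 | Cohorts starting utomilumab in Cycle 1 |
|---|---|---|
| Pre-dose | trough after 1 dose | trough after 2 doses |
| End of infusion | Cmax of dose 2 | Cmax of dose 3 |

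**Grid against footnotes.** If a site followed the Table 4 grid, an ADA sample exists on day 1, before any utomilumab, and serves as a baseline. If it followed footnote 36, none exists. First-dose Cmax needs an end-of-infusion sample on day 29, and neither source schedules one.

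**Size of the ADA problem.** Inputs are the pre-treatment positivity rates in Section 1.2.2.6 and the 20 patients planned for A10 in Section 9.3.1.4. Expected pre-existing positives = 20 × p; chance of at least one = 1 − (1 − p)^20.

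| Source | p | Expected among 20 | Chance of at least one |
|---|---|---|---|
| Study B1641001, Portion A | 9/61 = 14.8% | 2.95 | 0.96 |
| Study B1641003 | 2/23 = 8.7% | 1.74 | 0.84 |
| Study B1641001, Portion B | 2/41 = 4.9% | 0.98 | 0.63 |

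These counts assume that all 20 planned patients were treated and sampled.

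**The case against.** The strongest reply is that this no longer matters much. Section 3.2.1 states that no further enrollment into A10 is planned, so rewording a footnote cannot recover a sample from a patient already past Cycle 2 Day 1. Objective response, DLT and the main safety analyses are untouched. Ctrough is intact, including the trough after the first dose, and Cmax is still measured from the second dose on. Section 9.5.4 defines no treatment-induced category and describes onset and duration only if data permit; ever-positive at any time point can still be computed. All of this stands, and it sets the limits of the point.

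A reader might infer three stronger things that the documents do not support.

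- **That the sequencing question depends on the missing samples.** Section 1.2.7.1.2 justifies A9 and A10 by the order of immune activation and possible clinical benefit. Efficacy and safety are assessed cohort by cohort, and no A9-versus-A10 comparison of first-dose exposure is planned.
- **That no A10 patient has an ADA baseline.** The Table 4 grid may have been followed at some sites.
- **That stored Cycle 2 Day 1 serum is a safe baseline.** Utomilumab is infused first. Footnote 19 refers to blood drawn after utomilumab and before avelumab, and Section 7.2 permits, but does not require, pre-dose PK samples for all products to be drawn before the first infusion. A tube labelled pre-dose for avelumab may therefore follow utomilumab. Only Cycle 1 Day 1 blood certainly precedes it. Retention cannot be confirmed either: parts of Sections 7.2 and 7.3 are redacted, and Section 7.4 has biomarker specimens destroyed if they are not moved to long-term storage.

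Closure does not dispose of the matter, because the data already collected will still be summarised. As the rules stand, Section 9.5.1 puts values from different dose numbers under one label, and Section 9.5.4 counts pre-existing antibody as on-treatment antibody.

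**Conclusion.** The schedule is wrong as written. Footnotes 26 and 36 start A10's utomilumab sampling 28 days after its first utomilumab dose, against 0 days for the other three cohort and drug pairs. If the footnotes were followed, A10 has no pre-dose utomilumab ADA sample. First-dose Cmax is missing whether the footnotes or Table 4 were followed. The trough after the first dose and the later samples are unaffected.

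The effect is confined to secondary PK and ADA endpoints in one closed cohort. The figure of about 1 to 3 expected pre-existing positives (0.98 to 2.95) is an upper bound at the quoted rates. It rests on full enrollment of 20, sampling of every patient on Cycle 3 Day 1, and rates carried over from other studies. The actual size of A10 is not stated. The point remains worth acting on because the remedy is cheap and changes how A10's ADA and Cycle 3 PK values should be read.

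**What to change.** Reconcile footnotes 26 and 36 and Table 4 so that A10's utomilumab PK (pre-dose and end of infusion) and ADA (pre-dose) sampling starts on Cycle 2 Day 1, its first utomilumab dosing day. Blood is already drawn at that visit, so no visit is added.

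For patients already treated:

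1. Use any Cycle 1 Day 1 utomilumab ADA sample drawn under the Table 4 grid.
2. Otherwise assay retained Cycle 1 Day 1 pre-dose serum for utomilumab ADA, where retention and consent allow. Use Cycle 2 Day 1 serum only if the recorded draw time precedes the utomilumab infusion.
3. If neither exists, report A10 utomilumab ADA without baseline or onset classification.
4. Leave A10 out of first-dose Cmax and accumulation-ratio summaries, and label its Cycle 3 Day 1 PK values by utomilumab dose number rather than pooling them by cycle and day.

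The cost is at most about 20 assays on stored serum, or a short reporting rule.

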Abbreviations: ACTH = adrenocorticotrophic hormone; ADA = anti-drug antibodies; AE = adverse event; C=Cycle; CT = computed tomography; ECG = electrocardiogram; ECOG PS = Eastern Cooperative Oncology Group performance status; FFPE = formalin-fixed paraffin-embedded; HBV = hepatitis B virus; HCV = hepatitis C virus; MRI = magnetic resonance imaging; PK = pharmacokinetics; RECIST = Response Evaluation Criteria in Solid Tumors; RNA = ribonucleic acid; TCR = T-cell receptor.

Table 11. Schedule of Activities: Combination F (F1: Avelumab plus CMP-001, F2: Avelumab plus CMP-001 and Utomilumab, F3: Avelumab plus CMP-001 and PF-04518600) – Safety and Efficacy Assessments (Phase 1b and Phase 2)

Protocol Activities	Screening ^[1]	Treatment												Post Treatment		
		CYCLE 1				CYCLE 2				CYCLES 3-23		CYCLES ≥24		End of Treatment/ Withdrawal ^[43]	Follow-Up (Day 30, Day 60, Day 90) ^[44]	Survival Follow Up
	≤28 Days prior to Randomization	Day 1	Day 8	Day 15	Day 22	Day 1	Day 8	Day 15	Day 22	Day 1	Day 15	Day 1	Day 15			
Visit Time Window (days)		(±) 2	(±) 2	(±) 2	(±) 2	(±) 2	(±) 2	(±) 2	(±) 2	(±) 2	(±) 2	(±) 7	(±) 7	(+) 7	(±) 3	
Informed Consent ^[2]	X															
Tumor History ^[3] , Medical History ^[4] , Baseline Signs & Symptoms ^[6]	X															
Randomization ^[18]		X														
Adverse Events ^[24] Concomitant Treatments ^[25]		Monitored and recorded continually														
Physical Examination ^[5]	X	X	X	X	X	X	X	X	X	X	X	As clinically indicated		X	X (Day 30)	
Vital Signs ^[8]	X	X	X	X	X	X	X	X	X	X	X	X	X	X	X (Day 30)	
ECOG PS ^[7]	X	X				X			X					X	X (Day 30)	
Contraceptive Check ^[9]	X	X				X			X		X		X	X	X (Day 90)	

Protocol Activities	Screening ^[1]	Treatment												Post Treatment		
		CYCLE 1				CYCLE 2				CYCLES 3-23		CYCLES ≥24		End of Treatment/ Withdrawal ^[43]	Follow-Up (Day 30, Day 60, Day 90) ^[44]	Survival Follow Up
	≤28 Days prior to Randomization	Day 1	Day 8	Day 15	Day 22	Day 1	Day 8	Day 15	Day 22	Day 1	Day 15	Day 1	Day 15			
Visit Time Window (days)		(±) 2	(±) 2	(±) 2	(±) 2	(±) 2	(±) 2	(±) 2	(±) 2	(±) 2	(±) 2	(±) 7	(±) 7	(+) 7	(±) 3	
Safety Labs/Measurements																
Hematology ^[10]	X	X	X	X	X	X	X	X	X	X	X	X	X	X	X (Day 30)	
Blood Chemistry ^[11]	X	X	X	X	X	X	X	X	X	X	X	X	X	X	X (Day 30)	
Coagulation ^[12]	X	As clinically indicated														
Serum/Urine Pregnancy Test ^[13]	X	X		X		X		X		X	X	X	X		X (Day 30)	
12-Lead ECG ^[14]	X	X				X								X		
HBV, HCV tests ^[15]	X															

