Serum for pharmacogenomic/ proteomic/metabolomic analysis ^[35]		X		X									
Plasma for pharmacogenomic/ proteomic/metabolomic analysis ^[36]	X	X										X	
PAXGene whole blood collection optimized for RNA analysis ^[37]	X	X		X		X	X	X				X	
Banked biospecimens ^[38]		X											
Blood for Anti-Qb antibodies ^[39]		X		X		X			X		X (C8 only)		
Blood for Avelumab immunogenicity (ADA) testing ^[40]		X				X			X		X (C6 and C10 only)		

Protocol Activities	Screening ^[1] ≤28 days prior to Randomization	On Treatment (1 Cycle=28 days)									Post Treatment		
		Cycle 1				Cycle 2		Cycle 3	Cycle 4	Cycle 5	Cycles 6, 8, 10	End of Treatment /Withdrawal [43]	Follow Up (Day 30, 60, 90) [44]
		Day 1	Day 8	Day 15	Day 22	Day 1	Day 15	Day 1	Day 1	Day 1	Day 1		
Blood for utomilumab immunogenicity (ADA) testing ^[41] (Combination F2)		X				X			X		X (C6 and C10 only)		
Blood for PF-04518600 immunogenicity (ADA) testing ^[42] (Combination F3)		X				X			X		X (C6 and C10 only)		

Footnotes for Schedule of Activities (Combination F)

1. **Screening:** To be obtained within 28 days prior to randomization.
2. **Informed Consent:** Must be obtained prior to undergoing any study-specific procedure.
3. **Tumor History:** To be collected within 28 days prior to randomization. Includes disease characteristics, information on prior regimens (including dosing and duration of administration, best response observed, and recurrence date), surgery, and radiation therapy.
4. **Medical History:** To be collected during the screening period. Includes history of diseases other than the primary tumor under consideration (active or resolved) and concomitant illnesses.
5. **Physical Examination:** Includes an examination of major body systems. Weight for the purposes of dose calculation will be recorded at screening and within 3 days pre-dose Day 1 of each cycle. Weight will not be collected at End of Treatment. Height will be measured at screening only. During treatment starting C24 D1 physical examination to be performed only when clinically indicated.
6. **Baseline Signs/Symptoms:** Patients will be asked about any signs and symptoms experienced within the 14 days prior to study entry (Study entry is defined as randomization date) and recorded on the Medical History case report form (CRF) page. During treatment any new or worsening conditions since baseline should be reported on the Adverse Event (AE) CRF.
7. **ECOG PS:** ECOG performance scale is available as [Appendix 2](#).

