16. **ACTH, cortisol and Thyroid Function Tests:** Basal morning (fasting) Adrenocorticotrophic hormone (ACTH) and cortisol and Thyroid function tests (free T4 [FT4], thyroid stimulating hormone [TSH]) will be performed at Screening, Cycle 3 Day 1 and every 12 weeks thereafter, End of Treatment (EOT) visit, and 30 days after last investigational product administration, and if clinically indicated. See [Section 7.1.4](#) for the list of the required Laboratory Tests.
17. Serum cortisol response to acute ACTH stimulation with a 250- μ g dose should be performed to establish the diagnosis of adrenal insufficiency if basal morning ACTH and cortisol results are suggestive of adrenal insufficiency (eg, cortisol level is low) at screening and when clinically indicated during treatment. The institutional standards should be followed. Patients with a history of adrenal insufficiency will require additional premedication before CMP-001 administration. See [Section 5.3.5.2](#)
18. **Randomization/Enrollment:** Patient number and dose level allocation via interactive response technology (IRT) operated by Pfizer Inc. Investigational product administration should begin within 7 days after randomization.

Protocol Activities	Screening ^[1] ≤28 days prior to Randomization	On Treatment (1 Cycle=28 days)								Post Treatment	
		Cycle 1			Cycle 2		Cycle 3	Cycle 4	Cycle 5	Cycles 6, 8, 10	End of Treatment /Withdrawal [43]
		Day 1	Day 8	Day 15	Day 22	Day 1	Day 15	Day 1	Day 1	Day 1	

19. **Avelumab Administration:** Treatment will be administered every 2 weeks in 4-week cycles (ie, 28-day cycles). Avelumab will be administered as a 1-hour intravenous infusion every 2 weeks (eg, Days 1 and 15 of each cycle). Avelumab infusion will be administered before the CMP-001 injection. See [Section 5.3.5.2](#) for details of timing of investigational product administration. On days when PK samples are taken, avelumab infusion will start after the pre-avelumab pharmacokinetic blood samples are drawn. Treatment will continue until disease progression is confirmed by the investigator, patient refusal, unacceptable toxicity, or until the study is terminated by the Sponsor, whichever occurs first. See [Section 5.3.5.3](#) for details of treatment after initial determination of radiological disease progression.

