5.1. Allocation to Treatment

Each combination will be evaluated in 2 study parts, Phase 1b and Phase 2. During Phase 1b and Phase 2 for all combinations, allocation of patients to specific dose levels or cohorts will be performed by an interactive response technology (IRT) system after patients have given their written informed consent and have completed the necessary baseline assessments.

The IRT system will also be used to assign a patient identification number, which will be used on all Case Report Form (CRF) pages and other study-related documentation or correspondence referencing that patient.

No patient shall receive study treatments until the investigator or designee has received the following information in writing from the Sponsor:

- Confirmation of the patient's enrollment;
- Specification of the dose level cohort for that patient, and
- Permission to proceed with dosing the patient.

The Sponsor or designee will notify the other sites of the inclusion of a new patient, and will inform study sites about the next possible enrollment date.

Study treatment in randomized cohorts must be initiated preferably on the day of randomization, but no later than 7 days after randomization.

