8.2. Reporting Period

For SAEs, the active reporting period to Pfizer or its designated representative begins from the time that the subject provides informed consent, which is obtained prior to the subject's participation in the study, ie, prior to undergoing any study-related procedure and/or receiving investigational product, through and including 90 calendar days after the last administration of the study treatment.

SAEs occurring to a subject after the active reporting period has ended should be reported to the sponsor if the investigator becomes aware of them; at a minimum, all SAEs that the investigator believes have at least a reasonable possibility of being related to study treatment are to be reported to the sponsor.

AEs (serious and non-serious) should be recorded on the case report form (CRF) from the time the subject has taken at least 1 dose of study treatment through 90 calendar days after the last administration of the study treatment.

If a patient begins a new anticancer therapy, the AE reporting period for non-serious AEs ends at the time the new treatment is started. Death and SAE must be reported if it occurs during the SAE reporting period after the last dose of study treatment, irrespective of any intervening treatment.

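### Combination F schedules baseline signs and symptoms only at Screening, although footnote 6 asks for the 14 days up to randomization, so non-serious symptoms that start or worsen before first dose have no scheduled baseline record

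*Protocol*

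**What the plan says.** For Combination F, Table 11 places "Baseline Signs & Symptoms" in one row with tumor history and medical history. The row carries a single mark, under Screening. Footnote 1 to that table sets the Screening window: "To be obtained within 28 days prior to randomization". Footnote 6 then has the site ask about "any signs and symptoms experienced within the 14 days prior to study entry (Study entry is defined as randomization date" and enter the answers on the Medical History CRF page. It also fixes what the record is for: "During treatment any new or worsening conditions since baseline should be reported on the Adverse Event (AE) CRF".

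Footnote 18 says "Investigational product administration should begin within 7 days after randomization". Section 5.1 is slightly tighter: "Study treatment in randomized cohorts must be initiated preferably on the day of randomization, but no later than 7 days after randomization".

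Section 8.2 has adverse events recorded on the CRF "from the time the subject has taken at least 1 dose of study treatment through 90 calendar days after the last administration". SAEs are reported from informed consent. Footnote 4 places Combination F medical history in the screening period as well.

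In Tables 3, 5, 7 and 9 (Combinations A, B, C and D) the same item is marked on Cycle 1 Day 1 and left blank at Screening.

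**The concern.** Table 11 and its own footnote do not fit together. The table allows the interview as early as 28 days before randomization, while the footnote wants a 14-day period that ends at randomization. A site that follows the table can ask the question before part or all of that period has happened.

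What is lost is the reference point for adverse events. Footnote 6 makes this record the baseline against which a condition counts as new or worsening. Section 9.6.2.1 counts as treatment-emergent those events that begin or increase in severity after first dose. If a non-serious symptom appears after the interview and before dosing, no form is scheduled to hold its pre-dose grade. Seen during treatment, it looks new relative to the recorded baseline, and whether it worsened after dosing cannot be read from the data.

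A consequence for dose-limiting toxicity (DLT) is possible. Cohorts F1 to F3 expand or stop on small counts: at most 1, exactly 2, or at least 3 of 6 patients. Section 3.3 exempts headache, fever, flu-like symptoms or hypotension of Grade 3 or lower in Combination F if they resolve to Grade 1 or lower within 24 hours. That rule is harder to apply if an unrecorded higher-grade symptom was already present before dosing.

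**Working it through.** The plan states no figure for this interval, so there is none to reproduce. The check is calendar arithmetic.

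**Inputs**
- s = days from the interview to randomization: 0 to 28 (Table 11, footnote 1).
- Look-back = 14 days ending at randomization (Table 11, footnote 6).
- t = days from randomization to first dose: 0 to 7, with 0 preferred (footnote 18; Section 5.1).
- CRF recording of adverse events starts at first dose (Section 8.2).

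**Formulas**
- Look-back days covered = max(0, 14 − s).
- Interval with no scheduled record of non-serious symptoms = s + t.

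**Results**

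| Interview before randomization (s) | Look-back days covered | Interval to first dose (t = 0 to t = 7) |
|---|---|---|
| 28 days | 0 of 14 | 28 to 35 days |
| 14 days | 0 of 14 | 14 to 21 days |
| 7 days | 14 − 7 = 7 of 14 | 7 to 14 days |
| 0 days | 14 of 14 | 0 to 7 days |

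An interview 14 to 28 days before randomization covers none of the required period, one at 1 to 13 days covers part, and only one on the day of randomization covers all of it. The longest unrecorded interval is 28 + 7 = 35 days and the shortest is 0.

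**After the change.** With the item taken on Cycle 1 Day 1 before dosing, the interval from interview to first dose is 0 days and all 14 look-back days have passed. If footnote 6 still ended the look-back at randomization, up to 7 days before dosing would remain outside the question as worded. The footnote therefore has to change along with the table cell.

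**The case against.** The strongest defence is that Screening is a window and not a fixed day. A site that takes footnote 6 seriously will hold or update the interview close to randomization, which Table 11 itself places in the Cycle 1 Day 1 column. Section 5.1 prefers dosing on that same day. The 35 days needs both windows at their outer limits. This stands as to size. It does not remove the conflict, because the table asks for nothing after Screening.

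Other records also help. Combination F repeats physical examination, vital signs and ECOG status on Cycle 1 Day 1, reports SAEs from consent, and records concomitant treatments from 28 days before study treatment. Exclusion criterion 20 limits persisting toxicity from prior therapy. These give partial cover, but none is a scheduled symptom inventory with grades.

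Some stronger readings are tempting, and the documents do not support them:
- **Symptoms present at first dose have no baseline record at all.** Those already present at the interview are recorded. The gap concerns non-serious symptoms that start or worsen afterwards.
- **Combinations A to D have no gap, so F cannot be compared with them.** Combination A's footnote 6 also ends the look-back at randomization for its randomized cohorts, which may start dosing up to 7 days later. Section 9.6.2 summarizes safety for each cohort and combination separately, and no comparison of F with A to D is planned.
- **DLT counts will be distorted.** A DLT must be attributable to an investigational product, and the non-hematologic criteria mostly require Grade 3 or higher. A symptom would have to arise in the gap, escape notice on Day 1 and then be misattributed.
- **These symptoms are frequent in this population before dosing.** The protocol gives no frequency for them in pretreated head and neck cancer, so nothing here relies on one.

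**Conclusion.** The point holds in a limited form. Followed as written, Table 11 cannot satisfy footnote 6 unless the interview takes place on the day of randomization. Non-serious symptoms that start or worsen between the interview and first dose then have no scheduled baseline record. That interval is at most 35 days, and shorter when the interview is later or dosing starts sooner. The likely effect is some misclassification of adverse events as new or worsening. An effect on a DLT call is possible but not shown.

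The schedule applies to all of the approximately 60 patients planned for Combination F. How many would have a symptom in the gap cannot be estimated from the protocol. Cohorts F1 to F3 share the schedule, so it does not favour one over another.

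This rests on two readings: that the single mark in the Table 11 row is for Screening only, and that Section 8.2 governs when CRF recording of adverse events begins. The correction is worth making because it affects the baseline for adverse event classification and costs little.

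**What to change.** In Table 11, separate baseline signs and symptoms from the row it shares with tumor and medical history, and mark it on Cycle 1 Day 1 before dosing, as in Tables 3, 5, 7 and 9. Alternatively, keep the Screening interview and add a pre-dose update on Cycle 1 Day 1. Reword footnote 6 so that the recorded period runs through to first dose and does not stop at randomization. Leave tumor history and medical history at Screening.

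The cost is one table entry and one footnote. The patient already attends on Cycle 1 Day 1, so no visit or procedure is added.
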